3 STUDY VARIABLES

3.1 Fetal and Pregnancy Variables

The following characteristics regarding the pregnancy and the fetus will be collected at inclusion and baseline fetal echo:

- Gestational age at primary diagnosis (weeks and days) (potential confounder)
- Year of diagnosis (potential confounder)
- Primary diagnostic hospital, city and country

Statistical Analysis Plan

Protocol No:

Effect of fetal aortic valvuloplasty on outcomes

- Average yearly case volume of center performing fetal intervention (potential confounder)
- Gestational age at baseline fetal echo (weeks and days) (potential confounder)
- Hospital, city and country where each echo was performed
- Maternal age
- Parity

Protocol

- Multiple pregnancy (potential confounder)
- Mother's body mass index (BMI) (potential confounder)
- Maternal comorbidities
- Maternal contraindications to fetal intervention
- Echo data (baseline fetal echo). Only those considered as potential confounders listed here (for a full set of variables for all three echoes, 2 fetal and 1 neonatal, please see the annotated eCRF):
 - Left ventricular end-diastolic diameter (mm and z-score) (potential confounder)
 - Left ventricular inlet length in diastole (mm and z-score) (potential confounder)
 - Mitral valve diameter, 4 ch view in end diastole (potential confounder)
 - Aortic valve annulus diameter (mm) (potential confounder)
 - Mitral valve inflow pattern (Biphasic; Fused; Monophasic; No inflow) (potential confounder)
 - LV:RV inlet length ratio (potential confounder)

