4 STATISTICAL METHODOLOGY

4.1 General Methodology

Continuous variables will be described by means, standard deviation (SD), median and range, and categorical by number and percentages.

Main analyses will be performed comparing FAV 1+2 versus no-FAV 1+2 groups on FAS_{ENR} population. Complementary analyses will be performed on FAS_{BIRTH}, PP_{ENR} and PP_{BIRTH}. Separate descriptive comparisons between FAV 1 vs no-FAV 1 and FAV 1 vs no-FAV 1+2 groups will also be performed.

Comparisons between the two groups with respect to demographics and baseline characteristics and safety data will be performed using Fisher's exact test for dichotomous variables, Mantel-Haenszel Chi-square test for ordered categorical variables, Chi-square test for non-ordered categorical variables, and Fisher's non-parametric permutation test for continuous variables.

Due to the non-randomised design, all analyses will be adjusted for confounders. It is important that all known confounders at the time of inclusion are defined. The main confounders will be gestational age at first diagnosis and at inclusion, morphology and hemodynamics of the fetal heart at the time of study inclusion and possibly some data about the mother's health which could have an impact on the chance of success with fetal intervention, such as BMI. Although the study is designed to minimize bias by using strict echocardiographic inclusion criteria, it will be necessary to analyse the groups at baseline carefully with respect to a number of selected echocardiographic variables describing the size and function of the left heart. If this analysis shows that, in spite of the strict inclusion criteria, there are significant differences between the groups regarding data that are at the same time risk factors for the studied outcomes the analyses will be adjusted for those additionally defined confounders besides the known ones. A sensitivity analysis will also be performed for the primary variable applying propensity score matching procedure (1:1 or 2:1 if possible) including all variables that are of importance (p<0.10 using logistic regression) for discrimination of FAV vs no-FAV group and those identified/known confounders in the adjusted analyses.

Known confounders are:

• Gestational age at primary diagnosis (earlier gestational age could indicate more severe disease, and might differ between countries and centres due to different

Protocol

Statistical Analysis Plan

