Effect of fetal aortic valvuloplasty on outcomes

Protocol No:

screening policies) and gestational age at inclusion. Most probably they are highly correlated and in that case the more influential of the two will be used.

Variables listed under 3.1 as potential confounders will be investigated whether they are important for discriminating FAV vs no-FAV and whether they are confounders (associated p<0.10 both to the group and the outcome).

Dichotomous outcome variables will be analysed using logistic regression, adjusted for identified confounders available at the time of study inclusion. Odds-ratios (OR) with 95% confidence intervals (CI) will be presented.

Time-to-event analyses will be performed using Cox proportional hazards models adjusting for identified confounders. Proportional hazards assumption will be checked by visually reviewing log(-log(survival)) vs log(time) graphs, and by adding interaction between treatment group and log(time) in the model, where significant interaction indicates non-proportionality. Other methods will be applied, e.g. Poisson regression for time varying data, allowing study of changes in treatment effects over follow-up time, in case non-proportionality of hazards occurs.

Time-to-event data will be described by using Kaplan-Meier technique.

The primary analyses for the FAV vs no-FAV group conducted on FAS_{ENR} population will be considered as confirmatory analyses and a total significance mass of 0.05 will be applied. The tests will be performed on the primary variable and the most important secondary variables using fix sequential testing procedure according to the following order:

1. Primary variable: Transplantation-free survival from fetal diagnosis to 2 years postnatal age, having a biventricular circulation without pulmonary hypertension at that time

2. Secondary variable: Transplantation-free survival from fetal diagnosis to 2 years of age

3. Secondary variable: Survival from fetal diagnosis to live birth at term (≥37 weeks)

4. Secondary variable: Proportion of included fetuses who have a biventricular circulation at neonatal hospital discharge

5. Secondary variable: Proportion of included fetuses who have a biventricular circulation at 2 years of postnatal age

This means that first test must be significant on 0.05 significance level in order to be able to further confirm the tests 2 to 5, and the second test must be significant on 0.05 level in order to be able to confirm tests number 3 to 5, etc.

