4.6 Efficacy Analyses

4.6.1 Primary Efficacy Analysis

Primary efficacy analysis, test between FAV vs no-FAV regarding transplantation-free survival from fetal diagnosis to 2 years postnatal age, having a biventricular circulation without pulmonary hypertension at that time, will be performed using logistic regression adjusted for confounders identified according to the section General Methodology above. OR with 95% CI will be presented. The primary analysis will be performed on FAS_{ENR} population and will compare FAV 1+2 versus no-FAV 1+2. This analysis will be included in the evaluation of the confirmatory tests. Complementary analyses will be performed on FAS_{BIRTH}, PP_{ENR}, PP_{BIRTH} populations, and on all populations comparing FAV 1 with no–FAV 1 and FAV 1 vs no-FAV 1+2.

Sensitivity analyses will be performed using Fisher's exact test comparing the FAV group with the matched no-FAV group obtained applying propensity score matching according to the description in General Methodology above, both on FAS and PP populations.

Vertical bar charts will be presented for graphical purpose.

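### The propensity score in the matched sensitivity analysis is selected by p<0.10 association with group, so prognostic echo variables can be left out while treatment-tied variables enter

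*SAP*

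**What the plan says.** SAP 4.1 (General Methodology) plans a propensity-matched sensitivity analysis of the primary variable, 1:1 or 2:1 if possible. The score is formed by "including all variables that are of importance (p<0.10 using logistic regression) for discrimination of FAV vs no-FAV group". A second clause of the same sentence then extends the set: "and those identified/known confounders in the adjusted analyses".

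The same section supplies the terms:
- **Candidates.** "Variables listed under 3.1 as potential confounders will be investigated whether they are important for discriminating FAV vs no-FAV". SAP 3.1 marks as potential confounders two gestational ages, year of diagnosis, intervention-centre volume, multiple pregnancy, maternal BMI and six baseline echo variables.
- **Identified confounders.** Candidates are tested for "whether they are confounders (associated p<0.10 both to the group and the outcome").
- **Known confounders.** The list holds only gestational age, at primary diagnosis and at inclusion: "Most probably they are highly correlated and in that case the more influential of the two will be used".

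SAP 4.6.1 fixes the test: "Sensitivity analyses will be performed using Fisher's exact test comparing the FAV group with the matched no-FAV group". No covariate adjustment within the matched set is stated. The SAP gives no caliper, matching algorithm or balance criterion. The primary analysis in SAP 4.6.1 is a confounder-adjusted logistic regression and does not use the score.

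**The concern.** A score meant to make an outcome comparison fair should balance the variables that predict outcome. Selecting on a p-value against group can fail in two ways.

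First, a prognostic variable with a moderate group difference can miss p<0.10 in a sample of about 150. It is then left out of the score and is balanced only by luck.

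Second, a variable that separates the groups but has no bearing on outcome is certain to enter if it passes the screen. It pushes the two score distributions apart, so fewer no-FAV cases find a partner, with no gain in prognostic balance.

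The matched comparison is the one alternative method of confounding control planned for the primary variable. The primary model also requires p<0.10 with group (and with outcome). A prognostic echo variable that misses the group screen is thus absent from the primary model and from its check. What is at stake is the precision and balance of that check.

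**Working it through.** **1. The plan's own figure.** The SAP gives no power for the matched analysis. It gives 91.8% for a two-sided Fisher test at 100 versus 50, 60% versus 30%, alpha 0.05 (SAP 1.5). Exact enumeration gives 92.7%, close to the stated value. This confirms the setting but does not bear on the selection rule.

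**2. What the rule selects.** Let G be the candidates with p<0.10 for group and Y those with p<0.10 for outcome. The score contains G, the identified confounders (G and Y together) and the known confounder. Since the overlap of G and Y lies inside G, the score is G plus gestational age. The second clause adds nothing else.

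**3. What the screen misses.** At 100:50 the standard error of a standardised mean difference is sqrt(1/100 + 1/50) = 0.173. An observed difference below 1.645 x 0.173 = 0.285 SD fails p<0.10 (normal approximation). For a true difference of 0.25 SD, 0.25/0.173 = 1.44, and the chance of failing is about Phi(1.645 - 1.44) = Phi(0.20) = 0.58.

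**4. A variable tied to treatment.** SAP 3.1 lists "Average yearly case volume of center performing fetal intervention (potential confounder"). Under SAP 1.2 every intervention case comes from a high-volume centre. Under SAP 1.4, no-FAV 1 subjects are counselled where FAV is neither performed nor referred for. The variable describes the delivery of the intervention, and the SAP does not say what value a no-FAV case takes.

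**5. Simulation A** (all strengths assumed): n=150, about 2:1, up to 1500 runs per setting, no treatment effect, 1:1 nearest-neighbour matching, caliper 0.2 SD of the logit score. The comparator is a fixed list of the true outcome predictors.

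| Two treatment-only variables, log OR per SD | No-FAV matched, SAP rule vs fixed | Mean absolute prognostic imbalance (SD) | Mean risk difference |
|---|---|---|---|
| 0 | 84% vs 83% | 0.14 vs 0.07 | 0.018 vs 0.001 |
| 0.5 | 77% vs 83% | 0.16 vs 0.07 | 0.021 vs 0.000 |
| 1.0 | 62% vs 84% | 0.20 vs 0.07 | 0.039 vs 0.004 |

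Identified confounders were a subset of G in every run, as step 2 requires. A strong outcome predictor weakly tied to group (log OR 0.2) entered the score in 19-26% of runs. Treatment-only variables with a group effect entered in 76-100%.

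**6. Simulation B** (all strengths assumed): exactly 100:50, prognostic values 0-0.3 SD apart, log OR about 0.3 per SD, same caliper.
- Mean absolute prognostic imbalance was 0.08-0.13 SD under the SAP rule against 0.06-0.08 SD with the fixed list, and larger in every scenario.
- Three treatment-only variables 0.6 SD apart: about 36 against 45 pairs, power 45-52% against 61-62%.
- Two treatment-only variables 0.4 SD apart: 40 against 43 pairs, power 55% against 61%.
- No treatment-only variables: power 65% against 62%, so no loss.
- Bias, in the three-variable setting: signed imbalance about 0.01 SD or less under both rules; risk difference 0.258 against 0.261 with a conditional log OR of 1.4, and 0.001 against 0.000 under the null; null rejection 1.3% for both.

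**7. What lost pairs cost.** Exact unadjusted Fisher power at 60% versus 30%, 1:1: 50 pairs 82.9%, 40 pairs 72.5%, 34 pairs 62.2%, 30 pairs 56.1%.

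**The case against.** Several stronger readings are tempting, and the documents do not support them.

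- **That the score ignores outcome predictors.** It does not. Any variable that passes the screens for both group and outcome is in it, and gestational age is always in. The gap is confined to prognostic variables that miss the group screen.
- **That pairs will be lost.** This depends on treatment-only variables being present and strong. Without them, neither simulation showed a material loss. The comparator also contains exactly the true predictors, which is a best case, and 2:1 matching was not simulated.
- **That the matched result is biased.** Simulation B shows no bias. Simulation A shows a mean risk difference of 0.018-0.039 with no true effect, but there all the confounders push in the same direction by construction. A repeat of it kept null rejection below 5%. The documents give no covariate strengths, so a systematic bias cannot be asserted.
- **That the primary result is in question.** The confirmatory test is the adjusted logistic model. Eligibility criteria are identical in both groups, and SAP 2.1.1 removes the high-risk subpopulation from the full analysis set.
- **That BMI and year of diagnosis are treatment-only and should go.** SAP 3.1 names both as potential confounders, and SAP 4.1 ties BMI to the chance of a successful intervention. Dropping them would trade possible confounding for a few pairs.

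It can also be said that SAP 4.1 counts the morphology and haemodynamics of the fetal heart among the main confounders, so the sponsor may mean the echo variables to be included. But the known-confounder list does not name them, and the rule as written admits them only through the group screen.

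These arguments limit the point to balance and efficiency in a sensitivity analysis. They do not remove it.

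**Conclusion.** The point holds as a matter of balance and efficiency in a non-confirmatory analysis. That the rule selects by group association plus gestational age follows from the SAP's own definitions and needs no assumption.

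The size does rest on assumptions: covariate strengths, a 0.2 SD caliper and 1:1 matching, none of which the SAP fully specifies. At exactly 100:50, mean absolute prognostic imbalance is about 0.08-0.13 SD against 0.06-0.08 SD with a fixed list. The other set of assumptions gives 0.14-0.20 against 0.07 SD. A material fall in pairs and power needs treatment-only variables. Intervention-centre volume is the one candidate that the documents clearly tie to treatment. Type I error inflation was not shown, and a general claim of bias is not supported. The change is still worth making because it costs almost nothing.

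**What to change.** In SAP 4.1, replace the p<0.10 discrimination rule for the propensity score by these statements:

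- Include, whatever their p-values, gestational age (keeping the SAP's rule for choosing between diagnosis and inclusion) and the six baseline echo variables of SAP 3.1: LV end-diastolic diameter, LV inlet length, mitral valve diameter, aortic annulus diameter, mitral inflow pattern and LV:RV inlet length ratio.
- Do not enter the case volume of the centre performing the intervention.
- Keep BMI, year of diagnosis and multiple pregnancy as candidates, unless the sponsor judges in advance, and records, that they do not affect outcome.

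The cost is a few sentences in the SAP. All these variables are already planned for collection. The score gains a few terms, and if no treatment-only variables exist, about one matched pair may be lost.

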4.2 Patient Disposition and Data Sets Analysed

The number of patients included in each of the FAS_{ENR}, FAS_{BIRTH}, PP_{ENR}, PP_{BIRTH}, and safety populations will be summarized for each treatment group. Patients who completed the study and who withdrew from study prematurely will also be presented with a breakdown of the reasons for withdrawal by treatment group.

4.3 Protocol Violations/Deviations

Major protocol deviations are those that are considered to have an effect on the analysis. The protocol violations will be continuously collected during the study. The clinical monitors of the study will review the list and the finalisation of the major protocol deviations will be done at the clean file meeting.

The number of patients with major protocol deviations will be summarized per treatment group.

4.4 Fetal, Pregnancy, Neonatal and Follow-up at 2 Years Variables

Protocol

Statistical Analysis Plan

Effect of fetal aortic valvuloplasty on outcomes

Protocol No:

Fetal, pregnancy, neonatal and follow-up at 2 years variables will be summarized by treatment group for the FAS and PP populations and analysed according to the methods described in section General Methodology above.

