## Electronic case report forms (eCRF)

There are 14 eCRF's:

1. eCRF Inclusion criteria

All inclusion and no exclusion criteria need to be satisfied for a case to be included.

2. eCRF Inclusion

Include case if inclusin/exclusion criteria satisfied.

3. eCRF Counselling on fetal aortic valvuloplasty

If councelling was performed and, if so, what the decision was.

4. eCRF Baseline fetal echo 23+0 - 31+6

The baseline fetal echo is performed between 23+0 and 31+6 weeks. If an intervention is performed, the last exam before the intervention should be used as baseline fetal echo.

5. eCRF Additional baseline fetal echo 23+0 - 31+6

In case there is a late descision to perform an intervention, after a baseline fetal echo has already been submitted, there is an option to add an additional baseline fetal echo in the system.

6. eCRF Fetal interventions

A new eCRF Fetal interventions should be added for each intervention performed.

7. eCRF Follow-up fetal echo 33+0 - 34+6

The follow-up fetal echo is performed between 33+0 and 34+6 weeks.

8. eCRF Neonatal - Birth

Gestational age and size at birth, mode of delivery and pharmacological support.

9. eCRF Neonatal - Echo

First full study after birth, and before the first postnatal intervention, surgery or cath (except emergency atrial septostomy)

10. eCRF Neonatal - Cardiac clinical diagnosis

Cardiac diagnoses before the first intervention, surgery or cath (except emergency atrial septostomy)

11. eCRF Neonatal - Neonatal discharge

Type of circulation and clinical diagnoses at discharge.

12. eCRF Follow-up at 2 years of age

Type of circulation, clinical diagnoses, pulmonary hypertension, neurological sequealae, somatic growth.

13. eCRF Postnatal procedures

All cardiac surgical and catheter interventional procedures from birth to 2 years follow-up

14. eCRF Subject termination

Reason for subject termination including completion at 2 years of age.

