2 STUDY POPULATIONS

2.1 Definition of Study Populations

2.1.1 Full Analysis Set for All Enrolled

Fetuses with severe MR and severe LA enlargement and/or intact or highly restrictive interatrial communication and/or cases with hydrops present at inclusion are all high-risk cases regarding survival, but may have a rather good prognosis if they survive the first critical period. It is likely they will be overrepresented in the FAV group to such a degree that it will be difficult to control for through propensity score matching. Therefore this subpopulation will be excluded from the full analysis set and analysed separately. Fetuses developing any of these conditions after inclusion will not be excluded from the full analysis set.

All enrolled fetuses that have satisfied inclusion/exclusion criteria and belong to FAV 1+2 and no-FAV 1+2 groups and not listed as belonging to the high-risk population described above will be included in the Full Analysis Set enrolled (FAS_{ENR}) population. Infants wrongly included in the study (not fulfilling all inclusion or fulfilling any of the exclusion criteria) will not be part of the FAS_{ENR} population, but will be described in the safety analyses. As detailed under 1.3.2, also subjects with exclusion criteria present at inclusion but diagnosed only after birth will be retrospectively excluded from the FAS_{ENR} population.

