2.1.6 Safety Population

All enrolled fetuses will be included in the safety population, also those wrongly included if such cases will exist.

Figure 5. Full analysis sets (FAS)

ToP=Termination of Pregnancy; IUD=Intrauterine Death; GW=Gestational Weeks; FAS=Full Analysis Set; FAV=Fetal Aortic Valvuloplasty

STATISTISKA KONSULTGRUPPEN	Statisti	cal Analysis Plan
Protocol: Effect of fetal aortic valvuloplasty on outcomes	Protocol No):
	Version: 1.0	Page 14 of 26

Figure 6. Per protocol populations (PP)

ToP=Termination of Pregnancy; IUD=Intrauterine Death; GW=Gestational Weeks; PP=Per Protocol; FAV=Fetal Aortic Valvuloplasty

Figure 7. Safety population

GW=Gestational Weeks; FAV=Fetal Aortic Valvuloplasty

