3.3 Follow-up at Two Years Variables

The following variables will be collected at two years follow-up.

- Age at follow-up (months)
- Weight (kg)
- Weight SDS
- Height (cm)
- Height SDS
- Type of circulation (univentricular or biventricular)
- Pulmonary hypertension if biventricular

STATISTISKA KONSULTGRUPPEN	Statisti	cal Analysis Plan
Protocol: Effect of fetal aortic valvuloplasty on outcomes	Protocol No	D:
	Version: 1.0	Page 17 of 26

- Detailed cardiac diagnosis
- Non-cardiac diagnoses
- Neurological sequelae
- List of all cardiac surgical and catheter procedures performed

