3.5.3 Fetal and maternal complications of fetal intervention

Safety of the prenatal procedure will be evaluated through the following variables:

- Intervention-related fetal death (defined as fetal death within 24 hours of procedure)
- Fetal death not directly related to the intervention, except termination of pregnancy
- Maternal complications to procedure (requiring intensive care or resulting in maternal death)
- Preterm delivery < 37 weeks
- Reasons for fetal or postnatal death

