7 LISTING OF TABLES AND FIGURES

Table	Table Title
Number	
1.1.1	Patient Disposition and Data Sets Analysed (FAS Enrolled Population)
1.1.2	Patient Disposition and Data Sets Analysed (FAS At Birth Population)
1.1.3	Patient Disposition and Data Sets Analysed (PP Enrolled Population)
1.1.4	Patient Disposition and Data Sets Analysed (PP At Birth Population)
1.2	Protocol Deviations Leading to Exclusion from PP Population (FAS Enrolled
	Population)
1.3.1	Fetal and Pregnancy Variables (FAS Enrolled Population)
1.3.2	Fetal and Pregnancy Variables (FAS At Birth Population)
1.3.3	Fetal and Pregnancy Variables (PP Enrolled Population)
1.3.4	Fetal and Pregnancy Variables (PP At Birth Population)
1.4.1	Neonatal Variables (FAS Enrolled Population)
1.4.2	Neonatal Variables (FAS At Birth Population)
1.4.3	Neonatal Variables (PP Enrolled Population)
1.4.4	Neonatal Variables (PP At Birth Population)
1.5.1	Follow-up at 2 Years Variables (FAS Enrolled Population)
1.5.2	Follow-up at 2 Years Variables (FAS At Birth Population)
1.5.3	Follow-up at 2 Years Variables (PP Enrolled Population)
1.5.4	Follow-up at 2 Years Variables (PP At Birth Population)
1.6.1	Fetal Medical and Surgical History (FAS Enrolled Population)
1.6.2	Neonatal Medical and Surgical History (FAS Enrolled Population)
1.7.1	Prior Medications (FAS Enrolled Population)
1.7.2	Concomitant Medications (FAS Enrolled Population)
2.1.1	Adjusted Analysis of Primary Efficacy Variable (FAS Enrolled Population)
2.1.2	Adjusted Analysis of Primary Efficacy Variable (FAS At Birth Population)
2.1.3	Adjusted Analysis of Primary Efficacy Variable (PP Enrolled Population)

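### Neurological sequelae at 2 years are compared by arm with no place for earlier deaths, outside the safety analyses, and in no FAS or subgroup table for high-risk fetuses

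*SAP*

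**What the plan says.** The protocol's section on electronic case report forms gives the content of the 2-year form as "Type of circulation, clinical diagnoses, pulmonary hypertension, neurological sequealae, somatic growth". No other form names a neurological outcome. SAP 3.3 opens with "The following variables will be collected at two years follow-up" and lists "Neurological sequelae" among the items. The item does not appear under the efficacy variables (SAP 3.4) or the safety variables (SAP 3.5).

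SAP 4.4 sets the analysis: "Fetal, pregnancy, neonatal and follow-up at 2 years variables will be summarized by treatment group for the FAS and PP populations". It adds that these variables are analysed by the General Methodology, so this is a between-arm analysis and not only a listing. The matching tables are 1.5.1 to 1.5.4, one for each FAS and PP set, beginning with "Follow-up at 2 Years Variables (FAS Enrolled Population)".

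The safety population is wider: "All enrolled fetuses will be included in the safety population, also those wrongly included if such cases will exist". SAP 3.5.3 introduces its list with "Safety of the prenatal procedure will be evaluated through the following variables", and neurological outcome is not on that list. It is not named in SAP 4.7 or in the titles of Tables 3.1 to 3.3.x.

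For fetuses that are high-risk at inclusion, SAP 2.1.1 expects over-representation in the FAV group and concludes: "Therefore this subpopulation will be excluded from the full analysis set and analysed separately". SAP 4.6.3 limits their separate output to primary and secondary outcomes.

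**The concern.** A finding at a 2-year visit exists only for a child alive to be examined. Unless a rule says otherwise, fetal and infant deaths drop out of the numerator and the denominator, and the two arms are compared in groups selected by survival.

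Survival could differ by arm. Fetal death within 24 hours of the procedure can occur only with FAV, and transplantation-free survival to 2 years is the second test in the confirmatory sequence. If FAV keeps alive frail fetuses who are then impaired, a survivors-only comparison reads as harm. If FAV loses frail fetuses, it reads as benefit. Adjusting for baseline confounders (SAP 4.1) does not remove this, because the selection happens after treatment.

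The second gap is who is covered. The group in which the SAP expects FAV cases to predominate is the group for which no FAS or subgroup table shows this outcome. The protocol says the results may lead existing programs to be continued or reconsidered, so an uninterpretable statement on neurological outcome would be a real loss.

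**Working it through.** The plan gives no rate, margin or power for neurological sequelae, so there is no figure of its own to reproduce. The power statements (91.8% and 98.7%) concern the primary composite and do not bear on this point.

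**Step 1. How the plan treats death elsewhere.**
- Primary variable (SAP 3.4.1): death counts as failure.
- Biventricular circulation at discharge and at 2 years (SAP 3.4.2): proportions of included patients.
- Neurological sequelae (SAP 3.3, 4.4): no denominator, and no rule for deaths or missed visits.

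**Step 2. What conditioning on survival can do.** All rates here are assumed. Let *a* be the share surviving under either strategy, *p* their sequelae risk without FAV, *h* the true change in that risk due to FAV, *q* the share who die only if FAV is done, and *r* the sequelae risk in that share if they survive.

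- Survivors, FAV: p + h
- Survivors, no-FAV: (a·p + q·r)/(a + q)
- Survivors-only difference, FAV minus no-FAV: h − q(r − p)/(a + q)
- Death-or-sequelae difference per enrolled fetus: q(1 − r) + a·h

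Central case: a = 0.70, p = 0.15, q = 0.10, r = 0.50, h = 0.
- Survivors: 15.0% against (0.105 + 0.050)/0.80 = 19.4%, a difference of −4.4 points. FAV looks protective although it has no neurological effect.
- Per enrolled fetus: 0.30 + 0.105 = 40.5% against 0.20 + 0.155 = 35.5%, a difference of +5.0 points.
- With the planned 100 and 50 fetuses, survivors number 70 and 40, and expected children with sequelae are 70 × 0.15 = 10.5 and 0.155 × 50 = 7.75.

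Range, with q = 5, 10, 15, 20% and r = 30, 50, 70% (12 scenarios):

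| Assumption | Survivors-only difference | Death-or-sequelae difference |
|---|---|---|
| FAV loses frail fetuses, h = 0 | −1.0 to −12.2 points | +1.5 to +14.0 points |
| Mirror case: FAV saves frail fetuses, h = 0 | +1.0 to +12.2 points | −1.5 to −14.0 points |

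With a true harm of +3 points in those who survive either way, the central case reads 18.0% against 19.4%, so the sign is reversed. It reverses in 8 of the 12 scenarios, and in 5 of 12 with +5 points. In the mirror case with a true benefit of 3 points, the central values give (0.70 × 0.12 + 0.10 × 0.50)/0.80 = 16.8% against 15.0%, again the wrong sign.

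The bias term q(r − p)/(a + q) is zero if q = 0 (survival does not differ) or r = p (the extra survivors carry the same risk).

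**Step 3. Whether a single composite would cure it.** Death or sequelae is d + (1 − d)s, where d is the death rate and s the sequelae rate in survivors. Assume deaths of 20% with FAV and 35% without, and sequelae in 30% and 14% of survivors:
- FAV: 0.20 + 0.80 × 0.30 = 44.0%
- No-FAV: 0.35 + 0.65 × 0.14 = 44.1%

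Sequelae among survivors more than double and the composite shows nothing. The states have to be seen separately.

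**The case against.** The strongest reply is that the SAP states no wrong rule. It is silent on the denominator, and survivors-only is an inference from the timing of the form. That is fair, but the inference is the natural one and nothing in the plan prevents it.

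Mortality is also reported by arm. Transplantation-free survival to 2 years is tested on FAS_ENR, and reasons for fetal or postnatal death are described on the safety population. A reader could therefore see a survival imbalance. This lowers the risk of being misled, but separate tables do not give death or impairment per enrolled fetus, and they leave the high-risk gap open.

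Four stronger readings are tempting, and the documents do not support them:
- *That this is the only long-term harm measure.* Reasons for postnatal death and all postnatal procedures to 2 years are described on the safety population, and non-cardiac diagnoses and growth are collected at 2 years. It is the only named neurological outcome.
- *That the trial expects FAV to change survival.* The hypothesis and the 60% against 30% assumption concern the whole composite, which could improve through type of circulation alone.
- *That high-risk fetuses are absent from every table of this variable.* Their exclusion is stated for the FAS. SAP 2.1.3 and 2.1.4 do not say whether the PP sets include them, and the PP figure is not available. Tables 2.4.1.3 and 2.4.2.3 do cover the high-risk subgroup under a FAS label, but only for primary and secondary variables.
- *That the declared safety objective goes unanswered.* Neurology is not among the safety variables it lists, so this is a gap in what was declared.

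**Conclusion.** The point holds in a limited form. As written, the arm comparison of neurological sequelae is in effect conditional on survival and open to survivor bias in either direction. It sits outside the safety analyses, and no FAS or subgroup table gives it for the high-risk fetuses.

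It would go too far to say the comparison is biased. That needs both a survival difference by arm and a different neurological risk in the extra survivors, and the documents establish neither. Under the assumed rates above, the distortion in survivors runs from 1.0 to 12.2 points and can reverse the sign of a true 3-point effect. These figures show what is possible; they are not estimates.

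The primary analysis is unaffected. This is an inexpensive improvement to safety reporting.

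**What to change.** 1. Add neurological sequelae at 2 years to SAP 3.5.3.
2. In SAP 4.7.3, report it on the safety population as four exclusive states per enrolled fetus and arm: dead by 2 years; alive with sequelae; alive without sequelae; not assessed. Split the table by high-risk status at inclusion. Count terminations of pregnancy on a separate line, since the protocol excludes them from analysis but asks for their number.
3. In Tables 1.5.1 to 1.5.4, label the survivor percentage as descriptive and conditional on survival, and print its denominator. State whether the PP sets include high-risk fetuses.
4. Optionally, add death or sequelae by 2 years on FAS_ENR as a supportive analysis, with its components beside it. It should not be the sole arm comparison, because a mortality difference can mask a rise in sequelae. It also needs a yes/no coding of sequelae, which these documents do not define.

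The cost is SAP wording and one extra descriptive table from data already collected. Cell counts in the high-risk stratum will be small, so that part can only be descriptive.
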